#### Assessment of Intensity

The investigator will make an assessment of intensity for each AE and SAE reported during the study using the DAIDS grading table Version 2.1, March 2017 (https://rsc.tech-res.com/docs/default-source/safety/daidsgradingcorrecetedv21.pdf) and assign it to 1 of the following categories:

- Mild: no or minimal interference with usual social & functional activities
- Moderate: greater than minimal interference with usual social and functional activities
- Severe: inability to perform usual social and functional activities. An AE that is assessed as severe should not be confused with an SAE. Severe is a category utilized for rating the intensity of an event; and both AE and SAE can be assessed as severe.
- Life Threatening: inability to perform basic self-care functions

An event is defined as "serious" when it meets at least 1 of the predefined outcomes as described in the definition of an SAE, NOT when it is rated as severe.

#### Assessment of Causality

- The investigator is obligated to assess the relationship between study intervention and each occurrence of each AE/SAE.
- A "reasonable possibility" of a relationship conveys that there are facts, evidence, and/or arguments to suggest a causal relationship, rather than a relationship cannot be ruled out.
- The investigator will use clinical judgment to determine the relationship.
- Alternative causes, such as underlying disease(s), concomitant therapy, and other risk factors, as well as the temporal relationship of the event to study intervention administration will be considered and investigated.
- The investigator will also consult the CIB and/or Product Information, for marketed products, in his/her assessment.
- For each AE/SAE, the investigator must document in the medical notes that he/she has reviewed the AE/SAE and has provided an assessment of causality.
- There may be situations in which an SAE has occurred and the investigator has minimal information to include in the initial report to VH/GSK. However, it is very important that the investigator always make an assessment of causality for every event before the initial transmission of the SAE data to VH/GSK.
- The investigator may change his/her opinion of causality in light of follow-up information and send an SAE follow-up report with the updated causality assessment.
- The causality assessment is 1 of the criteria used when determining regulatory reporting requirements.

#### Follow-up of AE and SAE

- The investigator is obligated to perform or arrange for the conduct of supplemental measurements and/or evaluations as medically indicated or as requested by VH/GSK to elucidate the nature and/or causality of the AE or SAE as fully as possible. This may include additional laboratory tests or investigations, histopathological examinations, or consultation with other health care professionals.
- If a participant dies during participation in the study or during a recognized follow-up period, the investigator will provide VH/GSK with a copy of any post-mortem findings including histopathology.
- New or updated information will be recorded in the originally completed CRF.
- The investigator will submit any updated SAE data to VH/GSK within 24 hours of receipt of the information.

#### 10.6.4. Reporting of SAE to VH/GSK

#### SAE Reporting to VH/GSK via Electronic Data Collection Tool

- The primary mechanism for reporting SAE to VH/GSK will be the electronic data collection tool.
- If the electronic system is unavailable, then the site will use the paper SAE data collection tool (see next section) in order to report the event within 24 hours.
- The site will enter the SAE data into the electronic system as soon as it becomes available.
- The investigator or medically-qualified sub-investigator must show evidence within the electronic CRF (e.g., check review box, signature, etc.) of review and verification of the relationship of each SAE to study intervention/study participation (causality) within 72 hours of SAE entry into the eCRF.
- After the study is completed at a given site, the electronic data collection tool will be taken off-line to prevent the entry of new data or changes to existing data.
- If a site receives a report of a new SAE from a study participant or receives updated data on a previously reported SAE after the electronic data collection tool has been taken off-line, then the site can report this information on a paper SAE form (see next section) or to the medical monitor by telephone.
- Contacts for SAE reporting can be found in the SRM.

#### SAE Reporting to VH/GSK via Paper CRF

- Facsimile transmission of the SAE paper CRF is the preferred method to transmit this information to the medical monitor.
- In rare circumstances and in the absence of facsimile equipment, notification by telephone is acceptable with a copy of the SAE data collection tool sent by overnight mail or courier service.
- Initial notification via telephone does not replace the need for the investigator to complete and sign the SAE CRF pages within the designated reporting time frames.
- Contacts for SAE reporting can be found in SRM.

# 10.7. Appendix 7: Genetics

#### **USE/ANALYSIS OF DNA**

- Genetic variation may impact a participant's response to study intervention, susceptibility, severity, and progression of disease. Variable response to study intervention may be due to genetic determinants that impact drug absorption, distribution, metabolism, and excretion; mechanism of action of the drug; disease etiology; and/or molecular subtype of the disease being treated. Therefore, where local regulations and IRB/IEC allow, a blood sample will be collected for DNA analysis.
- DNA samples will be used for research related to GSK3640254 or HIV and related diseases. They may also be used to develop tests/assays including diagnostic tests related to GSK3640254 or HIV MIs and HIV. Genetic research may consist of the analysis of 1 or more candidate genes or the analysis of genetic markers throughout the genome or analysis of the entire genome (as appropriate).
- DNA samples will be analyzed if it is hypothesized that this may help further understand the clinical data.
- The samples may be analyzed as part of a multi-study assessment of genetic factors involved in the response to GSK3640254 or study interventions of this class. The results of genetic analyses may be reported in the clinical study report or in a separate study summary.
- The sponsor will store the DNA samples in a secure storage space with adequate measures to protect confidentiality.
- The samples will be retained while research on GSK3640254 (or study interventions of this class) or HIV continues but no longer than 15 years after the last participant's last visit or other period as per local requirements.

## 1. INTRODUCTION

The purpose of this reporting and analysis plan (RAP) is to describe the analyses to be included in the Clinical Study Report for Protocol: 208134

## 2. SUMMARY OF KEY PROTOCOL INFORMATION

This is an open-label, single-sequence, one-way drug interaction study to investigate the effect of GSK3640254 on the pharmacokinetics (PK) of tenofovir alafenamide (TAF) and emtricitabine (FTC). Treatment of human immunodeficiency virus (HIV) infection frequently involves combination therapy. It is important to understand any interactions and resulting changes in exposure (if any) when HIV medications are given in combination. Data from this study will contribute to dosing recommendations when GSK3640254 and TAF/FTC are given in combination.

[figure not shown]
## 2.1. Changes to the Protocol Defined Statistical Analysis Plan

There were no changes or deviations to the originally planned statistical analysis specified in the protocol (Dated: 27/DEC/2018).

## 2.2. Study Objective(s) and Endpoint(s)

Objectives		End	Ipoints			
Primary Objective	s	Primary Endpoints				
on the PK of Tomestabolite of T	AF, FTC, and the active AF prodrug, TFV under		AUC from Time 0 to the End of the Dosing Interval at Steady State (AUC(0- $\tau$ )) and Maximum Observed Concentration (Cmax) for TAF AUC(0- $\tau$ ), Cmax, and C $\tau$ for FTC and TFV			
Secondary Object	ives	Sec	ondary Endpoints			
TAF/FTC admi when coadmini	nistered alone and	•	Safety and tolerability parameters for Adverse Events (AEs)/Serious Adverse Events (SAEs), observed and change from baseline clinical laboratory assessments, electrocardiograms (ECGs), and vital sign measurements			
GSK3640254 i	e the steady-state PK of n the presence of althy participants	•	AUC(0- $\tau$ ), Cmax, C $\tau$ , and Time of Maximum Observed Concentration (Tmax) for GSK3640254			
TAF, FTC, and	TFV alone and in th GSK3640254 in	•	Tmax for TAF, FTC, and TFV			

## 2.3. Study Design

## 2.4. Statistical Hypotheses

No formal research hypothesis that will be statistically tested in this study.

Coadministration of GSK3640254 and TAF and FTC may increase the exposure of TAF, FTC, and the metabolite TFV, and coadministration of GSK3640254 with TAF and FTC are expected to have no significant impact on the exposure of GSK3640254.

Analyses will be performed on the natural logarithms of AUC(0- $\tau$ ), C $\tau$  and Cmax using linear mixed-effect models with period as a fixed effect, participants as random effect, and measurements within participant as repeated measures. Effects will be estimated, and confidence intervals (CIs) will be constructed for the following treatment comparisons:

• Period 2 versus Period 1 (TAF, FTC, and TFV)

## 3. PLANNED ANALYSES

## 3.1. Final Analyses

The final planned primary analyses will be performed after the completion of the following sequential steps:

- 1. All participants have completed the study as defined in the protocol.
- 2. All required database cleaning activities have been completed and final database release (DBR) and database freeze (DBF) has been declared by Data Management.

#### 4. ANALYSIS POPULATIONS

Population	Definition / Criteria	Analyses Evaluated
Screened	All participants who signed the informed consent form	
 
Study Population
 

Safety	
 
All participants who received at least 1 dose of study medication.
 
This population will be used for all demographic and safety summaries
 
	

Study Population

Safety

Pharmacokinetic Concentration	
 
All participants who underwent plasma PK sampling and had evaluable PK assay results.
 
This population will be used for the PK concentration listings, summary tables, and plotting of concentration-time data.
 
	PK Concentration
Pharmacokinetic Parameter	
 
All participants who underwent plasma PK sampling and had evaluable PK parameters estimated.
 
This population will be used for PK parameter listings, summary tables, and statistical analysis tables.
 
	

PK Parameter

PK statistical analysis

Refer to Appendix 9: List of Data Displays which details the population used for each display.

#### 4.1. Protocol Deviations

Important protocol deviations (including deviations related to study inclusion/exclusion criteria, conduct of the trial, participant management or participant assessment) will be summarised and listed.

Protocol deviations will be tracked by the study team throughout the conduct of the study in accordance with the Protocol Deviation Management Plan dated 11MAR2019. The "significant" protocol deviation in the Protocol Deviation Management Plan is equivalent to "important" protocol deviations.

- Data will be reviewed prior to freezing the database to ensure all significant deviations and deviations which may lead to exclusion from the analysis are captured and categorised on the protocol deviations dataset.
- This dataset will be the basis for the summaries and listings of protocol deviations.

A separate listing of all inclusion/exclusion criteria deviations will also be provided. This listing will be based on data as recorded on the inclusion/exclusion page of the electronic case record form (eCRF).

# 5. CONSIDERATIONS FOR DATA ANALYSES AND DATA HANDLING CONVENTIONS

## 5.1. Study Treatment & Sub-group Display Descriptors

Treatment Group Descriptions									
Data Displays for Reporting									
Description Code Order in TLF									
TAF/FTC 25/200 mg QD on Days 1 through 14 in Period 1	TAF/FTC	1							
TAF/FTC 25/200 mg QD + GSK3640254 200 mg QD on Days 1 through 7 in Period 2	TAF/FTC+GSK3640254	2							

### 5.2. Baseline Definitions

For all endpoints (except as noted in baseline definitions), the baseline value will be the latest pre-dose assessment with a non-missing value, including those from unscheduled visits. If time is not collected, Day 1 assessments are assumed to be taken prior to first dose and used as baseline. Baseline is applied to each treatment period.

Parameter	Study As	sessment Basel	s Considered as ine	Baseline Used in Data Display					
	Screening	Day -1	Day 1 (Pre-Dose)	Period 1 Period 2					
Safety									
Vital Sign	Х	Х	X	Day 1 (Pre-Dose) for each period					
12-Lead ECG	Х	Χ	Х	Day 1 (Pre-Dose)[1] for each period					
Hematology	Х	Х		Day -1 Period 1 Day 14					
Clinical Chemistry	Х	Х		Day -1 Period 1 Day 14					
Urinalysis	Х	Χ		Day -1	Period 1 Day 14				

 The average (for quantitative assessments) or the worst case (for interpretation) of the predose triplicate assessments on Day 1 of Period 1 will be used as the baseline for Period 1. The average (for quantitative assessments) or the worst case (for interpretation) of the predose triplicate assessments on Day 1 of Period 2 will be used as the baseline for Period 2.

Unless otherwise stated, if baseline data is missing no derivation will be performed and baseline will be set to missing.

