# 7.1.2. QTc Stopping Criteria

The *same* Fridericia QT correction formula (QTcF) *must* be used for *each individual participant* to determine eligibility for and discontinuation from the study. This formula may not be changed or substituted once the participant has been enrolled.

- The Baseline QTcF should be based on averaged QTcF values of triplicate ECGs obtained over a brief (e.g., 5-10 minute) recording period from the Day 1 pre-dose ECG.
- A randomized participant that develops an on-treatment QTcF >500 msec or an increase from baseline QTcF >60 msec should have two repeat unscheduled ECG's within 10 minutes. Using these triplicate ECGs, if the average QTcF >500 msec or an increase from baseline QTcF >60 msec, the participant will be withdrawn from the study. Finally, this participant should have repeated unscheduled ECGs until their QTcF measurement returns to their original averaged QTcF value at Day 1 pre-dose.

See the SoA (Section 1.3) for data to be collected at the time of intervention discontinuation and follow-up and for any further evaluations that need to be completed.

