#### 8.2.3. Electrocardiograms

- On Period 1, Day 1 and Period 2, Day 1, triplicate ECGs will be taken prior to dosing. The ECGs should be recorded over a brief (e.g., 5 to 10 minutes) recording period. Each measurement will be recorded in the CRF.
- Single 12-lead ECG will be obtained at other time points as outlined in the SoA (Section 1.3) using an ECG machine that automatically calculates the heart rate and measures PR, QRS, QT, and QTcF intervals. Refer to Section 7.1.2 for QTcF withdrawal criteria and additional QTcF readings that may be necessary.
- Twelve-lead ECGs will be performed with the participant in a supine or semi-supine position after a rest of at least 10 minutes.
- At each time point at which triplicate ECGs are required, 3 individual ECG tracings should be obtained as closely as possible in succession, but no more than 2 minutes apart. The full set of triplicates should be completed over a brief (e.g., 5 to 10 minutes) recording period.

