Amylase (Total), High	1.1 to < 1.5 × ULN	1.5 to < 3.0 × ULN	3.0 to < 5.0 × ULN	≥ 5.0 × ULN
Aspartate Aminotransferase, High	1.25 to < 2.5 × ULN	2.5 to < 5.0 × ULN	5.0 to < 10.0 × ULN	≥ 10.0 × ULN
Bicarbonate, Low (mEq/L; mmol/L)	16.0 to < LLN 16.0 to < LLN	11.0 to < 16.0 11.0 to < 16.0	8.0 to < 11.0 8.0 to < 110.	< 8.0 < 8.0
Direct Bilirubin, High > 28 days of age	NA	NA	> ULN with other signs and symptoms of hepatotoxicity	> ULN with life-threatening consequences (e.g., signs and symptoms of liver failure)
Total Bilirubin, High > 28 days of age	1.1 to < 1.6 × ULN	1.6 to < 2.6 × ULN	2.6 to < 5.0 × ULN	≥ 5.0 × ULN
Calcium, High (mg/dL; mmol/L)	10.6 to < 11.5	11.5 to < 12.5	12.5 to < 13.5	≥ 13.5
≥ 7 days of age	2.65 to < 2.88	2.88 to < 3.13	3.13 to < 3.38	≥ 3.38
Calcium, Low (mg/dL; mmol/L)	7.8 to < 8.4	7.0 to < 7.8	6.1 to < 7.0	< 6.1
≥ 7 days of age	1.95 to < 2.10	1.75 to < 1.95	1.53 to < 1.75	< 1.53
Creatine Kinase, High	3 to < 6 × ULN	6 to < 10 × ULN	10 to < 20 × ULN	≥ 20 × ULN
Creatinine, High Choose the method that selects for the higher grade	1.1 to 1.3 × ULN	> 1.3 to 1.8 × ULN OR Increase to 1.3 to < 1.5 × participant's baseline	> 1.8 to < 3.5 ULN OR Increase to 1.5 to < 2.0 × participant's baseline	≥ 3.5 × ULN OR Increase of ≥ 2.0 × participant's baseline
Glucose Fasting, High (mg/dL; mmol/L)	110 to 125 6.11 to < 6.95	> 125 to 250 6.95 to < 13.89	> 250 to 500 13.89 to < 27.75	≥ 500 ≥ 27.75
Glucose, Low (mg/dL; mmol/L) ≥ 1 month of age	55 to 64 3.05 to < 3.55	40 to < 55 2.22 to < 3.05	30 to < 40 1.67 to < 2.22	< 30 < 1.67
Lipase, High	1.1 to < 1.5 × ULN	1.5 to < 3.0 × ULN	3.0 to < 5.0 × ULN	≥ 5.0 × ULN
Cholesterol, Fasting, High (mg/dL; mmol/L) ≥ 18 years of age	200 to < 240 5.18 to < 6.19	240 to < 300 6.19 to < 7.77	≥ 300 ≥ 7.77	NA
Triglycerides, Fasting, High (mg/dL; mmol/L)	150 to 300 1.71 to 3.42	> 300 to 500 > 3.42 to 5.7	> 500 to < 1.000 > 5.7 to 11.4	> 1,000 > 11.4
Phosphate, Low (mg/dL; mmol/L) > 14 years of age	2.0 to < LLN 0.65 to < LLN	1.4 to < 2.0 0.45 to < 0.65	1.0 to < 1.4 0.32 to < 0.45	< 1.0 < 0.32
Potassium, High (mEq/L; mmol/L)	5.6 to < 6.0 5.6 to < 6.0	6.0 to < 6.5 6.0 to < 6.5	6.5 to < 7.0 6.5 to < 7.0	≥ 7.0 ≥ 7.0

Clinical Chemistry				
	Grade 1	Grade 2	Grade 3	Grade 4
Potossium Low (mEa/L: mmol/L)	3.0 to < 3.4	2.5 to < 3.0	2.0 to < 2.5	< 2.0
Potassium, Low (mEq/L; mmol/L)	3.0 to < 3.4	2.5 to < 3.0	2.0 to < 2.5	< 2.0
Codina High (mFa/L)	146 to < 150	150 to < 154	154 to < 160	≥ 160

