## 10.9.5. Safety Tables

Safety:	Tables				
No.	Population	IDSL / Example Shell	Title	Programming Notes	Deliverable [Priority]
Advers	e Events (AEs)			•	
2.1.	Safety	AE1CP	Summary of Adverse Events by System Organ Class and Preferred Term		SAC
2.2.	Safety	AE1CP	Summary of Drug-Related Adverse Events by System Organ Class and Preferred Term		SAC
2.3.	Safety	AE3	Summary of Common (>=5%) Adverse Events by Overall Frequency		SAC
2.4.	Safety	AE15	Summary of Common (>=5%) Non-serious Adverse Events by System Organ Class and Preferred Term (Number of Subjects and Occurrences)		SAC
2.5.	Safety	AE16	Summary of Serious Adverse Events by System Organ Class and Preferred Term (Number of Subjects and Occurrences)		SAC
2.6.	Safety	AE5A	Summary of Adverse Events by System Organ Class and Preferred Term and Maximum Intensity		SAC
Labora	tory: Chemistry	/			•
2.7.	Safety	LB1	Summary of Clinical Chemistry Changes from Baseline		SAC
2.8.	Safety	LB16	Summary of Clinical Chemistry Results by Maximum Grade Increase Post-Baseline Relative to Baseline		SAC
Labora	tory: Hematolo	gy		•	
2.9.	Safety	LB1	Summary of Hematology Changes from Baseline		SAC
2.10.	Safety	LB16	Summary of Hematology Results by Maximum Grade Increase Post-Baseline Relative to Baseline		SAC

Safety: Tables						
No.	Population	IDSL / Example Shell	Title	Programming Notes	Deliverable [Priority]	
Labora	tory: Urinalysis	,				
2.11.	Safety	UR3	Summary of Urinalysis Dipstick Results		SAC	
2.12.	Safety	LB1	Summary of Urine Concentration Changes from Baseline		SAC	
2.13.	Safety	LB16	Summary of Urinalysis by Maximum Grade Increase Post- Baseline Relative to Baseline		SAC	
ECG						
2.14.	Safety	EG1	Summary of ECG Findings		SAC	
2.15.	Safety	EG2	Summary of ECG Changes from Baseline		SAC	
2.16.	Safety	EG10	Summary of Maximum QTc Values Post-Baseline Relative to Baseline by Category		SAC	
2.17.	Safety	EG11	Summary of Maximum Increase in QTc Values Post-Baseline Relative to Baseline by Category		SAC	
Vital Si	gns					
2.18.	Safety	VS1	Summary of Vital Sign Changes from Baseline		SAC	
C-SSR	S					
2.19.	Safety	CSSRS4	Listing of C-SSRS Suicidal Ideation and Behavior Data	Only include participants who have suicidal ideation or behavior	SAC	

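### SAP 5.2 measures Period 2 safety changes only from an on-TAF/FTC baseline, so a rise built up over both periods can miss the baseline-relative creatinine and QTc thresholds

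*SAP*

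**What the plan says.** SAP 5.2 sets a general rule, "For all endpoints (except as noted in baseline definitions), the baseline value will be the latest pre-dose assessment with a non-missing value", and adds "Baseline is applied to each treatment period". For hematology, chemistry and urinalysis, the Period 1 and Period 2 baselines in the table read "Day -1 Period 1 Day 14". For ECG, the average of the "predose triplicate assessments on Day 1 of Period 2 will be used as the baseline for Period 2". Protocol 4.1 specifies no washout between periods, so every Period 2 baseline is taken on TAF/FTC.

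Two SAP appendices use thresholds relative to baseline, and neither names a different reference:

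- **Creatinine (10.6.1).** Grade 2 includes a rise to 1.3 to <1.5 times baseline, Grade 3 reads "Increase to 1.5 to < 2.0" times baseline, and Grade 4 starts at 2.0 times. A second branch uses ULN: Grade 1 from 1.1 x ULN, Grade 2 above 1.3 x ULN. The higher grade counts.
- **QTc (10.7.1).** The flags are an increase above 60 msec and, independently of baseline, an absolute value above 450 msec. Table 2.17 is the "Summary of Maximum Increase in QTc Values Post-Baseline Relative to Baseline by Category".

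Protocol 7.1.2 takes its QTcF baseline from the Day 1 predose ECG and follows a participant until QTcF "returns to their original averaged QTcF value at Day 1 pre-dose". It names no period. Protocol 8.2.3 creates two such sets: "On Period 1, Day 1 and Period 2, Day 1, triplicate ECGs will be taken prior to dosing".

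**The concern.** A secondary objective is the safety of TAF/FTC alone and with GSK3640254. Protocol 4.2 describes TAF and FTC as excreted mainly by the kidneys, and protocol 2.3 names QTc prolongation as a major risk of GSK3640254. Creatinine grade and QTc increase are therefore displays that readers will look at closely.

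When baseline is reset between periods without a washout, a rise that accumulates over both is split in two, and each part can fall below a threshold that the whole exceeds. No Period 2 table or figure in SAP 10.9.5 or 10.9.6 shows the total change from pre-study.

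The ECG schedule adds to this. On-treatment ECGs in Period 1 are planned on Day 1 only. The next is the Period 2 Day 1 predose triplicate, which becomes the new baseline. Any drift over Period 1 Days 2 to 14 is absorbed into that baseline.

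**Working it through.** The plan states no figure on this point, so there is none to reproduce. The inputs are the SAP 5.2 baselines and the thresholds in SAP 10.6.1 and 10.7.1. The documents give no creatinine ULN, so creatinine is expressed in multiples of ULN.

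**Creatinine: no grade in either period.** Let s be the Day -1 value divided by ULN. Three conditions must hold:

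1. Day 14 / Day -1 < 1.3
2. Period 2 value / Day 14 < 1.3
3. every value < 1.1 x ULN

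Conditions 1 and 2 cap the total ratio at 1.3 x 1.3 = 1.69. Condition 3 caps it at 1.1/s. The limit is the smaller of the two, and ungraded rises lie just under it.

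| s | 1.1/s | Limit on ungraded rise from Day -1 |
|---|---|---|
| 0.60 | 1.833 | 69% |
| 0.65 | 1.692 | 69% |
| 0.70 | 1.571 | 57% |
| 0.75 | 1.467 | 47% |
| 0.80 | 1.375 | 37.5% |
| 0.85 | 1.294 | 29% |
| 0.90 | 1.222 | 22% |
| 1.00 | 1.100 | 10% |

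The full 69% needs s at or below 1.1/1.69 = 0.65. From s = 1.1/1.3 = 0.846, the ULN branch gives a grade before the total rise reaches 30%, so the reset no longer decides whether a value is graded. It can still lower the grade. Take 0.85 to 1.05 to 1.29 x ULN: the period ratios are 1.24 and 1.23, so Period 2 is Grade 1 by ULN, but 1.29/0.85 = 1.52 would be Grade 3 against Day -1.

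Ungraded example: 0.60 to 0.768 to 0.983 x ULN. Each step is 1.28, so neither period has a grade. The total is 1.28 x 1.28 = 1.638, which is Grade 3 against Day -1.

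Listings 20 and 21 cover only graded results and participants who have one. This creatinine would not be listed individually unless another chemistry result in that participant was graded.

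**QTc: neither flag raised.** The total rise must exceed 60 msec with a final value no higher than 450 msec. The pre-study value must then be below 450 - 60 = 390 msec. Example: 375 to 415 to 445 msec.

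- From pre-study: 445 - 375 = +70
- From the Period 2 baseline: 445 - 415 = +30
- Absolute: 445, not above 450

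From 390 msec upwards, any rise above 60 takes the value past 450 and is flagged. Listing 28 shows all ECG values in every case.

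**Would replacing the period baseline be better?** Take creatinine 0.70 to 0.56 to 0.76 x ULN. Against the period baseline, 0.76/0.56 = 1.36, Grade 2. Against Day -1, 0.76/0.70 = 1.09 and the value is below 1.1 x ULN, so it has no grade. Replacement would lose a rise that arose on the combination.

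**Grading against both baselines.** Any Period 2 rise of 30% or more from Day -1 becomes at least Grade 2, so the limit on an ungraded rise falls from just under 69% to just under 30%, and the example above is still caught.

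**The case against.** The strongest case on the other side is that the period baseline is deliberate and correct. GSK3640254 is given only in Period 2, QTc prolongation is named as a risk of that drug and not of TAF/FTC, and the second triplicate exists so that its added effect can be isolated. All of that stands. That the two treatment columns start from different states follows from the fixed-sequence design.

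The documents also do not say that the thresholds are meant relative to an untreated value; they say only baseline. Investigators must review laboratory reports and record clinically relevant changes as AEs, whatever the SAP grades. Safety is descriptive, with about 16 healthy volunteers, and large cumulative rises may be uncommon.

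Several stronger readings are tempting, but the documents do not support them:

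- **A 69% rise can pass unnoticed in anyone.** The ULN branch limits this to low starting values.
- **69% is the ceiling for the combination alone.** It is the ceiling for no grade in both periods. If a Period 1 grade is allowed, Period 2 can be ungraded up to just under 1.1/s, for example +83% from 0.60 x ULN.
- **QTc rises are hidden.** The 450 msec flag and Listing 28 remain.
- **The withdrawal rule misses such rises.** Protocol 7.1.2 names no period, so this cannot be determined.

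What remains is the missing second comparison and the unstated reference.

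**Conclusion.** The point holds as a gap in the displays; the period baseline itself is not an error. SAP 5.2 gives Period 2 an on-TAF/FTC baseline, and nothing planned shows change from pre-study. The gap is just under 69% for creatinine at starts up to about 0.65 x ULN and narrows above that. For QTc it is confined to pre-study QTcF below 390 msec.

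Low creatinine starts are plausible here. By the protocol's MDRD formula without the 1.212 factor, a 50-year-old woman at the 80 mL/min limit has a creatinine of about 0.765 mg/dL. That is 0.64 x ULN if ULN is 1.2 mg/dL and 0.77 if it is 1.0, both assumed. The Cockcroft-Gault alternative can admit higher values.

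The conclusion assumes that baseline in SAP 10.6.1 and 10.7.1 means the 5.2 period baseline, which is the natural reading but is not stated there. The categories of Table 2.17 are not given in the documents. This is a worthwhile, inexpensive improvement, and it does not affect the primary PK analysis.

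**What to change.** - Keep the period baseline for all current displays.
- In SAP 5.2, define an additional study baseline: the last value before the first TAF/FTC dose (Day -1 for laboratory data, Period 1 Day 1 predose for ECG).
- For Period 2, add a Table 2.17 column for maximum QTc increase from the study baseline.
- Grade Period 2 creatinine against both baselines, take the higher grade and show which baseline triggered it. Do not replace the period baseline.
- State in SAP 10.6.1 and 10.7.1 which baseline applies.
- Reconcile protocol 7.1.2, protocol 8.2.3 and SAP 5.2 on which Day 1 triplicate is the QTc reference.

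The cost is SAP wording, one derived baseline variable, one table column and a trigger flag, plus a protocol clarification. No new data are needed. The small downside is that some grades in the combination column may partly reflect change that arose on TAF/FTC alone, which is why the triggering baseline should be shown.
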